**Table 1 - Protocol amendment statistical changes**

Amendment Number	Date Approved	Rationale	Description of statistical changes
1	28-May-2018	Type of AEs to be summarized during the on-study period, as well as the definition, were clarified	All AEs, SAEs, AEs leading to permanent treatment discontinuation, and AEs leading to death will be summarized for the on-study period
2	30-Jul-2018	To harmonize the anti-drug antibodies (ADA) endpoint with the other efpeglenatide Phase 3 clinical protocols	Change of ADA objective/endpoint from secondary objective/endpoint to tertiary/exploratory objective/endpoint
		Section 9.4.3 describes statistical analysis of secondary endpoints and the ADA endpoint has been moved to tertiary/exploratory endpoint	Removal of Table 9 describing the statistical analysis of ADA

## **1.6 STATISTICAL MODIFICATIONS MADE IN THE STATISTICAL ANALYSIS PLAN**

Not applicable.

## 2 STATISTICAL AND ANALYTICAL PROCEDURES

### 2.1 ANALYSIS ENDPOINTS

#### **Key definitions:**

**Completion of Study:** as study approaches to the end, the team will make prediction of time window when the target 330 first occurrence of 3-point MACE (positively adjudicated) can be achieved. Once projected visit window is determined, the site will be notified of the time window. Following announcement of the project study close-out visit:

- 1) for subjects remaining on IMP at announcement of project study close-out visit, sites will schedule a study close-out visit and an off-drug follow-up visit as per the time and events scheduled in protocol;
- 2) for subjects that have prematurely and permanently discontinued IMP prior to announcement of the project study close-out visit but still in study at the announcement, sites will schedule a study close-out visit;
- 3) for subjects that have prematurely and permanently discontinued study prior to announcement, sites will be required to make a final contact for efficacy outcome collection (if patients allow further contact by family member and health provider) or vital status check (if allowed by local law) as soon as possible after the announcement.

**Scheduled study-close out visit:** a study visit window projected by the sponsor during which the sites are required to bring all patients back to site for study closeout. It is a fixed calendar time window. For patients who already discontinued study prematurely, they'll miss this visit and their efficacy events after this scheduled visit will not be included for efficacy analysis even positively adjudicate.

**Scheduled last study visit:** later of study closeout visit or follow-up visit. That is, for patients still on IMP at study close-out visit, their scheduled last study visit will be follow-up visit; while for patients not on IMP at study close-out visit, study close-out visit will be their scheduled last study visit.

**End of study date:** defined as date of last scheduled visit for those completed the study (follow-up visit or study closeout visit if premature discontinued IMP) and the date collected on eCRF form 'Completion of End of Study' for those who did not complete study. If death is reason collected on the 'Completion of End of Study', date of death will be used

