7.3 LOST TO FOLLOW UP

A participant will be considered as potential lost to follow-up if he or she repeatedly fails to return for scheduled visits and is unable to be contacted by the study site.

The following actions must be taken if a participant fails to return to the clinic for a required study visit:

- The site must attempt to contact the participant and reschedule the missed visit as soon as possible and counsel the participant on the importance of maintaining the assigned visit schedule and ascertain whether or not the participant wishes to and/or should continue to take IMP or permanently discontinue IMP while still continuing attend study visits.
- Before a participant is deemed potential lost to follow up, the Investigator or designee must make every effort to regain contact with the participant (where possible, at least 3 telephone calls and, if necessary, a certified letter to the participant's last known mailing address or local equivalent methods, contact patient's family or private physician, review available registries, or health care DBs). These contact attempts should be documented in the participant's medical record and continue until DB lock.

The patient informed consent should mention that the study organization including the Sponsor will make every possible effort to determine this vital status during the scheduled duration of the study.

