### 1.3 DETERMINATION OF SAMPLE SIZE

It is estimated that approximately 4000 participants are needed to obtain approximately 330 participants with a positively adjudicated event for the primary composite cardiovascular endpoint (3-point MACE), based on the following trial design characteristics assumptions:

[figure not shown]
- A recruitment period of approximately 12 months
- Study duration is estimated to be approximately 24 months of follow-up after the last randomized patient, estimated follow-up ranging from 24 to 36 months
- 2% annual early study discontinuation
- Yearly event rate in placebo group: 4.4% for participants not using a SGLT2 inhibitor, and 3.7% for participants using a SGLT2 inhibitor
- Treatment effect of efpeglenatide compared to placebo: 15% risk reduction for participants not using a SGLT2 inhibitor, and a neutral effect for participants using a SGLT2 inhibitor
- 20% of participants using a SGLT2 inhibitor at baseline, and additional 10% participants in placebo group and 5% participants in efpeglenatide group adding a SGLT2 inhibitor during the study period

This will provide:

- 90% power to demonstrate non-inferiority (NI) of efpeglenatide vs placebo with a 1.3 NI margin {upper bound of the 95% CI of the estimated hazard ratio <1.3} for the 3-point MACE (CV death, non-fatal MI or non-fatal stroke)
- >99% power to demonstrate NI with a 1.8 margin

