#### **2.3.4.1 Analysis of primary efficacy endpoint(s)**

##### **2.3.4.1.1 Statistical Hypotheses**

The statistical hypothesis for the primary endpoint of 3-point MACE is to test that efpeglenatide is noninferior (1.8 and 1.3 margin) to placebo at the two-sided 5% alpha level:

- H0: Hazard ratio of efpeglenatide (pooled 4mg and 6mg groups) versus placebo  $\geq 1.8$  vs.  
Ha: Hazard ratio of efpeglenatide versus placebo  $< 1.8$

and

- H0: Hazard ratio of efpeglenatide (pooled 4mg and 6mg groups) versus placebo  $\geq 1.3$  vs.  
Ha: Hazard ratio of efpeglenatide versus placebo  $< 1.3$

The time to the first occurrence of the composite 3-point MACE endpoint (CV death, non-fatal MI, non-fatal stroke) will be analyzed using a Cox proportional hazards model with treatment (efpeglenatide 4 mg, efpeglenatide 6 mg, placebo), region (Norther America, Latin America, Europe, other), and randomization stratum of use of an SGLT2 inhibitor (current use, potential future use, neither current nor potential future use) as the factors. The analyses will be performed by including only events positively adjudicated by the CEC. Participants who receive either 4 mg or 6 mg of efpeglenatide will be combined as one efpeglenatide treatment group when making comparisons using appropriate contrast for the purposes of the primary analysis. The hazard ratio between pooled efpeglenatide and placebo will be estimated along with the associated 2-sided 95% CI. The NI with the 1.8 and 1.3 margin will be demonstrated on the primary endpoint if the upper bound of the 2-sided 95% CI is less than 1.8 and 1.3, respectively.

The time to event will be calculated as date of event as determined by the CEC (or date of censoring) – randomization date +1.

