##### **2.3.4.1.2 Censoring rule**

Patients will be right-censored at the last date with information available on the CV outcomes if they have not experienced any positively-adjudicated component of the primary composite CV events on or before their end of study visit. Specifically, the censoring date is defined as follows:

- Patients who completed the study will be censored at their scheduled last study visit date (study close-out visit date or final follow-up visit date)
- Patients who died before completing or discontinuing the study (ie, death reported on the Completion of End of Study form) will be censored at their date of non-CV death

- Patients who discontinued the study will be censored at their later of study discontinuation date or latest date with cardiovascular efficacy endpoint information (MI/UA, heart failure, cerebrovascular event, admission to hospital/emergency room, coronary procedure, or cardiac biomarkers as collected in eCRF) collected. For more details of censoring rule, please refer to [Appendix C](#).

Kaplan-Meier curves of the cumulative incidence rate will be provided by treatment groups over on-study efficacy period (from randomization to end of study date). The incidence rate per 100 patient-years (calculated by 100 \* number of patients with events / sum of time at risk (days) over all patients/365.25) will be reported. For patients with an event, patient-year is time from randomization to first event; for patient without any event, patient-year is from randomization to censoring date.

Underlying assumptions of the Cox proportional hazards model will be checked by visual inspection of the Kaplan-Meier plots (log(-log(survival)) vs log(survival time)).

Individual components of the primary endpoints will be analyzed using the same Cox proportional hazards model described above. Censoring rules described above will be used, and for components other than CV death, patients who died before completing or discontinuing the study will be censored at date of death (i.e. CV or non-CV death). See [Appendix C](#) for specific censoring rules.

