### ***Censoring***

The underlying rule for censoring is that the censoring date should be the last date the patient is known to be free of the event endpoint (free of each component for composite endpoint) on or before study close-out visit.

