***b. Specific censoring rule for all-cause mortality***

Patients who did not die will be censored at the latest date of: study close-out visit date, date of vital status (if alive), or date last known to be alive (if LTFU). Usually, this is the date of 'Date of last available information' in 'Subject Status' form for patient alive at that date.

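### The SAP's MACE censoring rule for study discontinuers conflicts with its own last-known-event-free principle, and for participants lost to follow-up it can count unobserved time as event-free

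*SAP*

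**What the plan says.** SAP 2.1 (Key definitions) takes the end of study date of a non-completer as "the date collected on eCRF form 'Completion of End of Study' for those who did not complete study". SAP 2.1.4 (Observation period) calls the same date the study discontinuation date.

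The operative rule for the primary endpoint is in SAP 2.3.4.1.2: "Patients who discontinued the study will be censored at their later of study discontinuation date or latest date with cardiovascular efficacy endpoint information". Appendix C, part a, repeats it. Neither place has a separate rule for participants lost to follow-up.

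Three other statements point the other way:

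- The general rule at the head of the Censoring part of Appendix C says that "the censoring date should be the last date the patient is known to be free of the event endpoint".
- The opening sentence of SAP 2.3.4.1.2, and Protocol 9.4.1 (Table 7), censor at the last date with information on the CV outcomes.
- For all-cause death, Appendix C, part b, lists the "date last known to be alive (if LTFU") among its censoring dates and points to a field on a separate Subject Status form.

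Protocol 7.3 describes repeated attempts to reach a missing participant: "These contact attempts should be documented in the participant's medical record and continue until DB lock". It does not say how the end-of-study form is to be dated.

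**The concern.** A participant who withdraws in person is in contact with the site on the discontinuation date, so that date is a fair end of observation. A lost participant is not. The site closes the case at some point after the last contact, and the form may carry either date. If it carries the closing date, a rule that takes the later of two dates selects a day on which nobody knew the MACE status.

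Two things would follow. Unobserved time would enter the primary Cox model as event-free time at risk. The same date also starts the missing-data work in SAP 2.3.4.1.3, so the gap would drop out of the analyses meant to test the effect of missing MACE data. The second consequence matters more: a tipping-point analysis cannot stress time that it treats as observed.

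**Working it through.** **1. The plan's own figure.** The documents give no figure for unobserved time before discontinuation. The nearest stated figure is the power, and it reproduces. Inputs from SAP 1.1, 1.3 and 2.3.4.1.1: "approximately 4000 participants are needed to obtain approximately 330" participants with an event; 1:1:1 allocation, so 2:1 for pooled efpeglenatide against placebo; a test of non-inferiority "to placebo at the two-sided 5% alpha level"; and "90% power to demonstrate non-inferiority (NI) of efpeglenatide vs placebo with a 1.3 NI margin".

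- Placebo rate, counting the added SGLT2 inhibitor users from day 1 (30% users): 0.70 × 0.044 + 0.30 × 0.037 = 0.0419.
- Efpeglenatide rate (25% users): 0.75 × 0.044 × 0.85 + 0.25 × 0.037 = 0.0373.
- HR = 0.0373 / 0.0419 = 0.890.
- SE of log HR = 1/√(330 × 1/3 × 2/3) = 0.1168.
- Power = Φ[ln(1.3/0.890)/0.1168 − 1.96] = 90.0%.

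If the added users count for half of follow-up, the HR is 0.883 and the power 91.2%. The censoring question does not change this calculation.

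**2. How the date passes through the analyses.** SAP 2.3.4.1.3 defines missing MACE data as events after the censoring date and summarises missing time from there to planned close-out. The Appendix D code computes survival from treatment end to `adt`, the censoring date, and draws event times only beyond it. Event-free status up to `adt` is therefore taken as known. Any draw later than close-out is reset to close-out as censored. If `adt` is already at or after close-out, every draw is reset: that participant gets no imputed events, and the hazard multiplier in the tipping-point analysis has nothing to act on.

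**3. Possible size.** The share of discontinuers who are lost, and the gap from last contact to form date, are assumptions; neither document gives them.

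- Discontinuers at 2% a year over a mean 2.5 years: 4000 × (1 − 0.98^2.5) = about 197.
- Total follow-up at the planned rates: about 9,290 patient-years, with about 0.039 events per patient-year.
- Unobserved time = 197 × share lost × gap in years.

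| Share lost | Gap | Patient-years | % of total | Expected unseen events |
|---|---|---|---|---|
| 25% | 3 months | 12 | 0.1 | 0.5 |
| 50% | 6 months | 49 | 0.5 | 1.9 |
| 100% | 12 months | 197 | 2.1 | 7.7 |

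The last row is generous, because a 12-month gap does not fit before close-out for someone lost in the final year. About 1/2.5 = 40% of discontinuers leave in that year and would have on average half a year left, so a cap at close-out gives about 197 × (0.6 × 1 + 0.4 × 0.5) = 158 patient-years.

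Mean time from discontinuation to close-out is about 1.28 years. Against that mean, a gap of 3, 6 or 12 months hides 0.25/1.28 = 20%, 0.5/1.28 = 39% or 1/1.28 = 78% of an affected participant's missing time.

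**4. Effect on the primary comparison.** If the gaps are balanced across arms, the HR hardly changes. The one-sided extreme puts all unobserved time in the efpeglenatide arms, which hold about two thirds of follow-up. Unobserved time of 1% (2%) of the total then inflates their follow-up by 1.5% (3%) and divides the HR by 1.015 (1.03). With 330 events the upper confidence bound is HR × exp(1.96 × 0.1168) = HR × 1.257.

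- HR 1.00: the bound falls from 1.257 to 1.239 (1.221).
- HR 1.04: the bound falls from 1.307 to 1.288 (1.269), across the 1.3 margin.

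The bound is below 1.3 only if the observed HR is below 1.3/1.257 = 1.034, so the conclusion could change only close to that value.

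**The case against.** The strongest reply is that the premise is not in the documents. No section says what date the form carries for a lost participant. Instructions for completing it would normally sit in CRF guidance, which is not part of the protocol or SAP. If sites enter the last contact, there is no bias.

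The plan also tries to recover outcomes. SAP 2.1 requires a final contact for those who left before the close-out announcement, through family or health provider where allowed. Protocol 7.3 adds registries and health-care databases. SAP 2.1.3 counts positively adjudicated events up to scheduled close-out even after discontinuation. Some apparently silent time would therefore be ascertained, which makes the patient-years above upper figures for any given share and gap.

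This reply rules out a stronger reading that a reader might infer: that the SAP deliberately prefers the form date to the last contact, so that silent time is certainly counted as observed. The SAP takes the later of two dates, and it states the opposite principle in two places. What it contains is a conflict between a general rule and a specific one.

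The conflict itself stands, and a late form date is plausible. Contact attempts run to database lock. Amendment 01 removed the statement that unreachable patients are considered withdrawn, so loss of contact does not itself produce a discontinuation date. Protocol 9.4.2, SAP 2.2 and Appendix C each name a last contact separately from end of study. Where a final or third-party contact does establish MACE status, the fix uses that date, so those efforts do not argue against it.

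**Conclusion.** The point holds as an internal contradiction with a conditional consequence. The specific rule in SAP 2.3.4.1.2 and Appendix C, part a, can give a censoring date that the general rule in Appendix C and Protocol 9.4.1 would not allow. Whether it does so depends on how the form is dated for lost participants, which the documents leave open.

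The range of 12–197 patient-years rests on an assumed 25–100% of discontinuers lost and an assumed gap of 3–12 months. It is not an estimate of what will occur. A reader might infer from the HR 1.04 example that the non-inferiority result is at risk. The documents do not support that: the example needs every gap to fall in the efpeglenatide arms of a double-blind trial and an observed HR near 1.034. The more likely harm is a missing-data assessment that understates missing follow-up and so looks more reassuring than it should. The rule should be corrected before database lock.

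**What to change.** In SAP 2.3.4.1.2 and Appendix C, part a, add a rule for participants lost to follow-up: censor MACE at the last visit, telephone contact or third-party contact at which cardiovascular outcome status was ascertained, capped at scheduled close-out. Do not use the form date. Use the same date as the start of missing time in SAP 2.3.4.1.3 (missing-time summary, imputation and tipping-point analysis) and as `adt` in Appendix D.

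Do not borrow the Subject Status field from the all-cause mortality rule, unless cardiovascular outcomes were also ascertained on that date. It is a vital-status date: a registry entry showing that someone is alive says nothing about a non-fatal MI or stroke, and using it would recreate the problem.

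The cost is SAP wording and one derived date. The documents do not show a dedicated field for the date of last known MACE status, so the sponsor should confirm that the date can be built from visit and contact records. The analysis will have slightly fewer patient-years and will report more missing follow-up.

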#### **2.1.1 Study completer: subjects completed study closeout visit (in person or by phone) or has died while in study Demographic and baseline characteristics**

The baseline value (with the exception of serum creatinine and estimated glomerular filtration rate [eGFR]) is defined generally as the last available value prior to the first dose administration of double-blind IMP or the last available value on or before the date of randomization for patients

who were randomized but never exposed to IMP. For lab parameters, only central lab values should be used for baseline value derivation.

For serum creatinine and eGFR, baseline is defined as the average of all central lab values before the first dose of the double-blind IMP for those randomized and exposed or before randomization for those who were randomized but never exposed to double-blind IMP.

All baseline safety and efficacy parameters (apart from those listed below) are presented along with the summary statistics in the safety and efficacy sections ([Section 2.3.4](#) and [Section 2.3.5](#)).

### ***Demographic characteristics***

Demographic variables to be summarized are:

- Age (years),
- Age groups (<50,  $\geq$ 50 and <65,  $\geq$ 65 and <75,  $\geq$ 75 years),
- Sex (Male, Female),
- Race (White, Black or African American, Asian, American Indian or Alaska Native, Native Hawaiian or Other Pacific Islander, Multiple, Unknown),
- Ethnicity (Hispanic or Latino, Not Hispanic or Latino, Unknown),
- Region (North America, Latin America, Europe, Other),
- Baseline body mass index (BMI) (kg/m^2),
- Baseline BMI categories (<30,  $\geq$ 30 to <40,  $\geq$ 40 kg/m^2),
- Baseline body weight (kg),
- Smoking status (never, current, former),
- Alcohol habit (never, occasional, at least daily, at least weekly, at least monthly).

### ***Medical or surgical history***

Medical (or surgical) history includes general medical or surgical history. This information will be coded using the version of Medical Dictionary for Regulatory Activities (MedDRA) currently in effect at Sanofi at the time of database lock.

### ***Disease characteristics at screening or baseline***

Specific disease history includes:

- Duration of diabetes (years) derived as: (Date of informed consent - Date of diagnosis of diabetes + 1)/365.25,
- Duration of diabetes categories (<10,  $\geq$ 10 years),
- Age at diagnosis of type 2 diabetes (years) derived as: Year of diagnosis of diabetes - Year of birth,

- Baseline HbA1c (%),
- Baseline HbA1c categories (<8%, ≥8%),
- Retinopathy history (Yes/No),
- Baseline eGFR (mL/min/1.73m^2),
- Baseline eGFR categories (<15 mL/min/1.73m^2 [End stage renal disease], ≥15 to <30 mL/min/1.73m^2 [Severe decrease in GFR], ≥30 to <60 mL/min/1.73m^2 [Moderate decrease in GFR], ≥60 to <90 mL/min/1.73m^2 [Mild decrease in GFR], and ≥90 mL/min/1.73m^2 [Normal]),
- Randomization strata of SGLT2 use (Current use, Potential future use, Neither current nor potential future use),
- Use of SGLT2 at baseline (yes, no),
- History of heart failure.

The following summary will also be provided:

- Baseline Serum creatinine (μmol/L),
- Baseline Systolic blood pressure (mmHg),
- Baseline Diastolic blood pressure (mmHg),
- Baseline Heart rate (beats per min),
- Baseline UACR (mg/g),
- Baseline lipid profile (total cholesterol, HDL, LDL, triglycerides),
- Patients with at least 1 CV risk factor at screening or baseline,
- History of cardiovascular disease (CVD) (e.g. Coronary artery disease [CAD], cerebrovascular disease, and peripheral vascular disease),
- CV risk factors.

Any technical details related to computation, dates, and imputation for missing dates are described in [Section 2.5](#).

### 2.1.2 Prior or concomitant medications

Any medication or vaccine (including over-the-counter or prescription medicines, vitamins, and/or herbal supplements) that the participant is receiving at the time of enrollment or during the study must be recorded in the corresponding case report form page.

All medications will be coded using the World Health Organization-Drug Dictionary (WHO-DD) using the version currently in effect at Sanofi at the time of database lock.

Medications will be classified into the following 3 groups:

- Prior medications are those the patient used prior to first IMP intake. Prior medications can be discontinued before first administration or can be ongoing during treatment phase.
- Concomitant medications are any treatments received by the patient concomitantly to the IMP(s), from first dose to the end of treatment + 30 days (+ 7 days for antidiabetic drugs). A given medication can be classified both as a prior medication and as a concomitant medication. Concomitant medications do not include medications started during the posttreatment period (as defined in the observation period in [Section 2.1.4](#)).
- Posttreatment medications are those the patient took in the period running from the 31st day (8 days for antidiabetic drugs) after the last injection of IMP up to the end of the study.

Any technical details related to computation, dates, imputation for missing dates are described in [Section 2.5](#).

